4.2.3 Exploratory Endpoints

N/A

5 Recruitment

Starting immediately after IRB approval and lasting for approximately 12 months, subjects will be acquired by convenience sampling. The Study Investigator ([name]) will recruit subjects via a participant registry maintained by the Principal Investigator ([name]). The participant registry includes both survivors of stroke and healthy control participants. The registry is maintained by the PI to "develop a resource that researchers can use to recruit healthy individuals and patients with stroke in IRB-approved studies conducted by the Mobilis Laboratory" (s18-00959). We may also recruit participants through word of mouth from other studies conducted in the PI's laboratory.

The patient's affected hand will be examined to determine if the patient's impairment satisfies inclusion/exclusion criteria in one of the NYULMC treatment rooms allocated for research activities. After it is determined that the subject is eligible to participate in the study, the consent process will proceed. During the consenting process, all subjects will have the purpose of the experiment, the complete procedure, and any potential risks involved in participation in the study explained to them by the investigators. Participants in the stroke group will receive a one-time \$50 check following their participation in our study. Healthy control participants will receive a one-time \$25 check. The reason for this difference in value is the potential for increased burden on stroke patients regarding transportation (i.e., some are not medically cleared to operate a motor vehicle) and care due to their impairment.

5.1 Inclusion Criteria

In order to be eligible to participate in this study, an individual must meet all of the following criteria:

Healthy controls

1. Having obtained the age of 18 years
2. Neurologically healthy (i.e., no history of: traumatic brain injury, peripheral neuropathy, seizures, etc.)
3. Strongly right-handed according to at least 80% score on the Edinburgh Handedness Inventory (Oldfield, 1971; Veale, 2013). The use of right-handed participants is a common feature in this field of study. This is due to the slight differences in arm control between left- and right-handed individuals (Sainburg & Kalakanis, 2000).
4. Ability to give informed consent

Survivors of stroke

1. Having obtained the age of 18 years
2. have a diagnosis of stroke more than six months prior to entry into the study;
3. have the ability to reach, unsupported, to approximately 70% of arm length
4. ability to give informed consent

5.2 Exclusion Criteria

An individual who meets any of the following criteria will be excluded from participation in this study:

All participants

1. have any conditions that limit their capability of using a Head Mounted Display (HMD) for a VR environment or cooperate with the protocol.
2. have any orthopedic injuries to the upper extremities.
3. Have neurological injuries other than stroke.
4. Have excessive pain in any joint of either arm that could limit the ability to cooperate with the protocols.
5. Visuospatial neglect
6. Apraxia
7. Global inattention
8. Legal blindness

5.3 Vulnerable Subjects

This study does not propose to enroll vulnerable subjects.

5.3.1 Adults without Capacity to Consent

This study will not recruit individuals with impaired consent capacity. We expect 0% of the contacted stroke participants to lack the capacity to consent. These patients will have already consented in the past; therefore, a formal capacity assessment is not warranted. Informal judgment that prospective participants have the capacity to consent will be made through routine interactions with the individual during the consent process. Capacity will be determined by the Study Investigator to assess the prospective participant's verbal understanding of the protocol including the purpose, objectives, potential risks and benefits of participation. We will explicitly ask them to recollect

the purpose, risks, and benefits after explaining and prior to their signing the consent form. We will not consent or enroll any individual suspected of diminished capacity to consent.

5.3.2 Assessment of Capacity

Assessment of capacity will be done by the Study Investigator, [name]. The assessors are study team members that are identified in Research Navigator.

The individual performing the assessment and/or monitoring ongoing capacity will perform the assessment through routine interaction with the prospective participant during the consent process.

The results of the capacity assessment will not be placed in the subject's medical record. Results will not be placed in the participant's medical record because we are not performing a formal capacity assessment.

Prospective subjects will be informed of the results of the capacity assessment after it's conducted. If an individual is found not to have the capacity to consent, the assessor will explain this to the individual. The assessor will provide the necessary resources and referrals for further care and evaluation.

5.3.3 Surrogate Consent

N/A. Enrolled participants will possess capacity and therefore not require a surrogate.

5.3.4 Ongoing Assessment of Capacity

At each study visit, subjects will have direct interaction with the Study Investigator, [name] or study team members identified in Research Navigator. If assessors have any concerns about the subject's capacity, a capacity assessment will be conducted as described above. Subjects who lose capacity will be withdrawn from the study. Subjects who appear to be unduly distressed will be withdrawn from the study.

5.4 Duration of Study Participation

Participants will be asked to participate in a single, 2-hour session. This includes enrollment, screening, and completion of the protocol requirements.

5.5 Total Number of Participants

Recruitment will end when approximately 24 participants are enrolled. It is expected that approximately 30 participants will be enrolled in order to produce 24 evaluable participants.

5.6 Participant Withdrawal or Termination

5.6.1 Reasons for Withdrawal or Termination

Participants are free to withdraw from participation in the study at any time upon request. An investigator may terminate participation in the study if:

- Any clinical adverse event (AE) or other medical condition or situation occurs such that continued participation in the study would not be in the best interest of the participant
- The participant meets an exclusion criterion (either newly developed or not previously recognized) that precludes further study participation
- The participant fails to adhere to protocol requirements
- Subject withdraws consent
- Subject experiences excessive fatigue or discomfort

Abrupt withdrawal or termination from study will not affect participant safety or clinical management.

5.6.2 Handling of Participant Withdrawals or Termination

The proposed study does not seek to obtain follow-up data. As such, withdrawn or terminated participants will not be contacted for further data collection for the given protocol. Replacement of withdrawn or terminated participants will follow with standard recruitment and retention policies outlined in 5.4 Strategies for Recruitment and Retention.

5.7 Premature Termination or Suspension of Study

This study may be temporarily suspended or prematurely terminated if there is sufficient reasonable cause. Written notification, documenting the reason for study suspension or termination, will be provided by the suspending or terminating party to the NYU IRB. If the study is prematurely terminated or suspended, the PI will promptly inform the IRB and will provide the reason(s) for the termination or suspension.

Circumstances that may warrant termination or suspension include, but are not limited to:

- Determination of unexpected, significant, or unacceptable risk to participants
- Insufficient compliance to protocol requirements
- Data that are not sufficiently complete and/or evaluable
- Determination of futility

Study may resume once concerns about safety, protocol compliance, data quality are addressed and satisfy the sponsor and/or IRB.

6 Study Device

6.1 Study Device

We designed a bilateral exoskeleton to apply a torque to the shoulder joint when participants reach for targets in a virtual reality environment. We use rubber bands to apply force to the upper arm about an axis of rotation pointing through the glenohumeral joint. The mechanics are designed to ensure the torque profile generated by the exoskeleton matches the torque profile generated by the force due to gravity through a range of motion from neutral (anatomical position) to 120 degrees of forward flexion. Our exoskeletons have two operating modes. In the gravity assistance mode, the torque vector points opposite (180 degrees) that of the gravity torque vector. In the gravity resistance mode, the torque vector points in the same direction (0 degrees) as the gravity torque vector. That is, torque profiles are equal to 50% in magnitude, but opposite in direction to that of gravity. We apply gravity assistance to the impaired arm (non-dominant for healthy controls) and gravity resistance to the non-impaired arm of our stroke participants.

This study will use two devices: an Oculus Rift Headset and a custom-built exoskeleton.

Oculus Rift headset: The Oculus Rift is a commercially-available virtual reality headset manufactured and sold by Meta Inc. It is used to present the visual environment in which participants perform the reaching task.

This is not a medical device in the context of the study since we are not evaluating the safety or efficacy of this device in the diagnosis of disease or other conditions, or in the cure, mitigation, treatment, or prevention of disease.

In addition the device is not intended to affect the structure or any function of the body.

Exoskeleton Device: The exoskeleton device was designed and constructed by the study investigator, [name]. The bilateral device is used to support the impaired arm (non-dominant in healthy controls) against gravity while simultaneously resisting movement of the non-impaired arm of stroke participants. We consider the device to be a non-significant risk device as it meets the criteria for an abbreviated IDE. Please see the “Appendix: Investigational Device” in the Devices section for justification.

6.1.1 Acquisition

The exoskeleton device was designed and constructed by the study investigator, [name]. This device is stored in a locked room on the NYULMC campus. The device will only be used by the study team for this study and no other study.

6.1.2 Formulation, Appearance, Packaging, and Labeling

We designed the exoskeleton in SolidWorks (Dassault Systems, Aachen, Germany). A schematic of the shoulder piece is shown in Figure 3. Planar pieces (e.g., arm piece) were laser cut from 1/4" acrylic. Volumetric pieces (e.g., arm holster) were 3D printed using ABS plastic.

[figure not shown]

Figure 3: Left shoulder exoskeleton device in assist mode. *Left panel:* Isometric view of the exoskeleton. *Right panel:* Sagittal view of the exoskeleton with arm holster removed.

The exoskeleton device is mounted to the participant testing chair using a custom-built frame. The frame was constructed from 1" T-slotted framing rails, which allowed us to raise and lower the exoskeleton device so that its axis of rotation aligned with the glenohumeral joint. We placed the participant's arm into the holster piece (Figure 3, left panel) and secured it using two Velcro straps. Rubber bands were looped around two needle-roller bearings to reduce friction. These rubber bands produced a force directed along a vector pointing from the distal needle bearing towards the proximal one, indicated by the red dashed line in Figure 3, right panel. In the configuration shown in Figure 3, the rubber bands produced a torque directed against gravity (assist mode). We could move the proximal needle bearing to the inferior portion of the device to produce a torque in the same direction as gravity (resist mode). The device is investigational and not commercially marketed.

6.1.3 Product Storage and Stability

The device will be stored at the offices of the study team in a locked testing room. The device does not expire.

6.1.4 Preparation

N/A. The agent is not an IDS.

6.1.5 Dosing and Administration

Based on the mechanics of the device, derived in our previous study (Brunfeldt et al., *in review*), we determined the number of rubber bands needed to produce 50% gravity compensation:

The final calculations yielded the following linear relationships

$$\tau_{assist} = 1.089N_{5\frac{7}{8}} + 0.16N_{7\frac{1}{8}} - 0.13 \text{ (Nm)}$$

and

$$\tau_{resist} = 0.722N_{5\frac{7}{8}} + 0.17N_{7\frac{1}{8}} + 0.7 \text{ (Nm)}$$

where N is the number of rubber bands with subscript indicating length and width (i.e., $N_{5''x5/8''}$ is the number of 5"x5/8" rubber bands). For example, the rubber band configuration for an individual with arm length of ~0.57m and weight ~75kg:

Assist mode: $5 \times 5'' \times 5/8'' + 2 \times 7'' \times 1/8'' = 5.64$ Nm, which is approximately 50.7% of the torque due to gravity of her fully outstretched arm.

Resist mode: $6 \times 7'' \times 5/8'' + 3 \times 7'' \times 1/8'' = 5.54$ Nm, which is approximately 49.8% of the torque due to gravity of her fully outstretched arm.

6.1.6 Route of Administration

The study device will be attached to the participant using Velcro straps. The device be supported by a metal frame attached to a chair in which the participant is seated. The device setup will be performed by the study investigator, [name].

6.1.7 Starting Dose and Dose Escalation Schedule

Starting dose is 50% gravity compensation. There is no escalation.

6.1.8 Dose Adjustments/Modifications/Delays

There will be no dose adjustment or modification.

6.1.9 Duration of Therapy

Study participants will complete all requirements within the single, 2-hour session. They will wear the device for no more than 15 minutes.

6.1.10 Tracking of Dose

Torque levels will be set by the study investigator on a per-participant basis, equal to 50% of the torque due to gravity.

6.1.11 Device Specific Considerations

- Device size. Approximately 1 meter, fully extended
- Device model. N/A. Custom, non-commercial device.
- Device settings and programming. 50% gravity compensation.
- Duration of implant or exposure. No more than 15 minutes.
- Frequency of exposure. One.

6.2 Study Agent Accountability Procedures

N/A. The study agent is not a pharmaceutical or investigational drug agent.

7 Study Procedures and Schedule

7.1 Study Procedures/Evaluations

Both stroke participants and healthy controls will participate in a single session. Both groups will undergo the same protocol with two exceptions. Stroke participants will be asked to provide permission to review their medical records; they will also perform the Fugl-Meyer Assessment if no recent score has been obtained.

Task	Stroke	Controls
Consent	X	X
Inclusion/exclusion	X	X
Demographic Information	X	X
Edinburgh Handedness Inventory – Short Form	X	X

Fugl-Meyer Assessment (as needed)	X	
Virtual Reality Task (with EMG and exoskeleton)	X	X
Access & download neuroimaging	X	

7.1.1 Study Specific Procedures

- *Medical history:* stroke information (date, location, hemorrhagic vs. ischemic)
- *Medication history:* None
- *Radiographic or other imaging assessments.* No new assessments will be acquired, but we will obtain standard of care imaging from hospital admission.
- *Biological specimen collection and laboratory evaluations. None*
- *A discussion of if the results of any study specific procedures (e.g., radiographic or other imaging or laboratory evaluations) will be provided to participant.* None.
- *Counseling procedures.* None
- *Assessment of study agent adherence.* N/A. No investigational agent
- *Administration of questionnaires or other instruments for patient-reported outcomes, such as a daily diary.* If participants do not have an Edinburgh Handedness Survey, one will be given to them. See Appendix.

7.1.2 Other Assays or Procedures

Fugl-Meyer Assessment and Edinburgh Handedness Inventory Questionnaire data will be used to screen for eligibility. The MOBILIS ([name]) laboratory registry contains these data (s17-00447, s18-00959).

7.2 Study Schedule

The study consists of a single, 2-hour session. It is typical for participants to finish within 90-150 minutes. All procedures are conducted ONLY for research purposes. No procedures will supplant standard of care. No procedures will interfere with standard of care.

Participants will be contacted via phone call or text message, during which the Study Investigator will provide the prospective participant with a synopsis of the purpose and objectives of the research, a brief description of the protocol, and any potential risks and benefits. The prospective participant will be verbally informed that participation is completely voluntary. Upon verbal agreement of the prospective participant, the Study Investigator will schedule the single visit at the participant's earliest convenience, usually within one-week of initial contact.

The Study Investigator will also ask verbal consent to view the prospective participant's medical records. We inform the participant that no data will be downloaded or collected about the medical record, only that we use this to screen those with acute MRI imaging and to obtain the Fugl-Meyer assessment score (see Section 6.1).

The single session will begin with the informed consent process. After obtaining consent, we will gather information about the participant (e.g., age, height, weight, etc.; see Section 10). We then administer the Edinburgh Handedness Inventory Short Form (Oldfield, 1971; Veale, 2013). We then let the participant practice with the VR headset; we attach the EMG sensors; we attach the exoskeletons. We then start data collection on the VR task protocol. Participants finish their participation with maximum voluntary contraction measurement. We then provide the participant with the appropriate stipend amount and ask them if they have any questions/concerns about their participation.

7.2.1 Screening

Screening Visit (Day -28 to -1)

- Contact potential participant via phone, text, SendSafe, or MyChart. Provide verbal information about purpose, objectives, procedures, any potential risks and benefits to participation
- Ask permission to access medical records. Study Investigator will screen for those participants with acute DWI neuroimaging in the NYULMC system. No data will be collected or downloaded at this point in the study. This is only for screening purposes.

- We will also determine if the participant has a recent Fugl-Meyer assessment (within 12 months). If no Fugl-Meyer score is available, the Study Investigator will administer the assessment during the visit (~15 minutes).
- Instruct participants that they are to wear or bring a short-sleeved shirt to the visit. This is so we can attach the EMG leads to the participant's arms.

7.2.2 Enrollment/Baseline

As this is a single-session observational study, enrollment, baseline, and testing is planned in the same visit.

Enrollment/Baseline Visit (Visit 1, Day 0)

- Obtain and document consent from participant on study consent form.
- Verify inclusion/exclusion criteria.
- Obtain demographic information.
- Edinburgh handedness survey
- Administer full protocol.

8 Assessment of Safety

8.1 Specification of Safety Parameters

No study endpoint are considered safety parameters. No safety parameters will be recorded. The dose of 50% gravity compensation has been used in our previous work with no reports of adverse events (Brunfeldt et al., 2022, Brunfeldt et al., *in review*).

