2.4 Potential Risks & Benefits

2.4.1 Known Potential Risks

Potential risks of the exoskeleton include arm fatigue and soft-tissue (e.g., muscle, skin) discomfort. Fatigue is not greater than minimal risk because the arm movements will mimic reaching for an object on a shelf at eye level. No more than 54 reaches will be made in any single testing block, and these reaches are self-paced. Soft-tissue discomfort may arise from the exoskeleton applying a force to the arm. Discomfort poses no greater than minimal risk because the participant will only wear the device for approximately 5 minutes during the data collection phase. Also, the magnitude of force applied to the arm is no more than 50% of that due to gravity. The upper arm weighs approximately 5.77% of body weight ((Plagenhoef et al., 1983). For example, a 150 lbs. person would receiving a loading amount to counter 8.65 lbs. of force. The exoskeleton device will be worn during all testing blocks, however, the load is only applied during the 'loading phase' which lasts approximately 5 minutes.

It is anticipated that participants may be inconvenienced by the amount of time necessary to complete the study and may experience fatigue because of completing required reaching tasks in the VR system. Very rarely, participants may experience short-term dizziness or headache because of using the head mounted display of the VR system. Participants will be given ample time for practice and rest, and they may take a break and/or discontinue the study at any time.

To limit the risks associated with VR headset and exoskeleton use, we will provide the participant with breaks every 5-minutes. Also, all reaches will be self-paced. Participants will be verbally instructed that they may request unscheduled breaks during the data collection blocks. These unscheduled breaks will not affect data integrity. We also use padding and elastic gauze on the arms to reduce pressure and abrasion risk.

There is a potential risk of breach of confidentiality. To mitigate this, procedures will be carried out in a laboratory space on the NYULMC campus. We are requesting personal health information from the patient's medical record. To mitigate this, access will only be granted to named persons on this protocol; data will be stored on TrialMaster.

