8.4 Reporting Procedures – Notifying the IRB

8.4.1 Adverse Event Reporting

At each contact with the subject, the investigator must seek information on adverse events by specific questioning and, as appropriate, by examination. Information on all adverse events should be recorded immediately in the source document, and also in the appropriate adverse event module of the case report form (CRF). All clearly related signs, symptoms, and abnormal diagnostic procedures results should be recorded in the source document, though should be grouped under one diagnosis.

All adverse events occurring during the study period must be recorded. The clinical course of each event should be followed until resolution, stabilization, or until it has been determined that the study treatment or participation is not the cause. Serious adverse events that are still ongoing at the end of the study period must be followed up to determine the final outcome. Any serious adverse event that occurs after the study period and is considered to be possibly related to study participation should be recorded and reported immediately.

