8.8 Safety Oversight

It is the responsibility of the Principal Investigator to oversee the safety of the study at his/her site. This safety monitoring will include careful assessment and appropriate reporting of adverse events as noted above, as well as the construction and implementation of a site data and safety-monitoring plan (DSMP). Medical monitoring will include a regular assessment of the number and type of serious adverse events.

Data Safety Monitoring Plan

Safety oversight will be under the direction of the study PI, [name] and the study investigator, [name]. The DSMP members will meet twice, once at the 6-month time point and again at the 12 month time point, to assess safety data on each arm of the study. Safety will be assessed by quantifying the number, percentage, magnitude, and frequency of:

- Headache
- Dizziness
- Arm soft-tissue discomfort
- Complaints (non-specific to anticipated risks)
- Breaches of confidentiality

There are no halting rules for this study. A summary of the outcomes of these safety reviews along with accumulated adverse events and deviations will be submitted to the IRB as part of an annual progress report at the time of the Continuing Review submission.

9 Clinical Monitoring

Clinical site monitoring is conducted to ensure that the rights and well-being of human subjects are protected, that the reported trial data are accurate, complete, and verifiable, and that the conduct of the trial is in compliance with the currently approved protocol/amendment(s), with GCP, and with applicable regulatory requirement(s):

- The NYU Human Research Protection Program may monitor the progress of the study. Monitoring will occur at the HRP's discretion on a random basis at any frequency it deems necessary to ensure compliance and study safety.
- Independent audits will not be conducted to ensure monitoring practices are performed consistently across all participating sites. This is a single-site study.
- Each clinical site will perform internal quality management of study conduct, data collection, documentation and completion. An individualized quality management plan will be developed to describe a site's quality management.

10 Statistical Considerations

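### Section 8.1 rules out recording safety data that 8.3, 8.4.1, 8.8 and 14.1 require, and the 8.8 review list leaves out arm fatigue

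*Combined protocol and SAP*

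**What the plan says.** Section 8.1 first says that none of the endpoints is a safety parameter. It then adds "No safety parameters will be recorded" and points to the absence of reported AEs in two earlier studies at the same compensation level.

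Section 8.8 sets up a safety review: "The DSMP members will meet twice, once at the 6-month time point and again at the 12 month time point". Of its content it says "Safety will be assessed by quantifying the number, percentage, magnitude, and frequency of" five items: headache, dizziness, "Arm soft-tissue discomfort", complaints outside the anticipated risks, and confidentiality breaches.

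Section 2.4.1 opens its list of risks with "Potential risks of the exoskeleton include arm fatigue and soft-tissue (e.g., muscle, skin) discomfort", and mentions fatigue again as a consequence of the reaching task. Section 5.6.1 includes among the grounds for ending participation "Subject experiences excessive fatigue or discomfort".

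Section 8.4.1 says that at each contact "the investigator must seek information on adverse events by specific questioning". In the visit narrative of 7.2, the only closing enquiry is that staff "ask them if they have any questions/concerns about their participation".

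**The concern.** Two things do not fit together. Staff who follow 8.1 literally would record nothing that the 8.8 review could count, while staff who follow 8.3 and 8.4.1 would record everything. A protocol should not leave that to the reader's choice of section.

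The risk that the protocol puts first for its own device is also missing from the list of items to be counted. The review will be the basis for any statement on how well the device was tolerated. If fatigue reaches it only when somebody classes it as an AE, while headache and dizziness have their own lines, the summary will be least systematic on the symptom most closely tied to loading the arm.

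**Working it through.** No formula tests this point. The check sets the sections side by side.

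**1. Is data to be recorded?**

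- 8.1: no safety parameters.
- 8.3: every AE is documented whatever its cause, with severity, onset and resolution.
- 8.4.1: AEs are asked about specifically at each contact, and all are recorded.
- 8.8: symptoms are counted and graded, and accumulated AEs go to the IRB with the review summaries.
- 14.1: AEs and data on expected adverse reactions are entered in the data capture system.

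Four sections require recording or depend on it; one denies it.

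**2. Which risks have an item in the 8.8 list?**

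| Participant-level risk in 2.4.1 | Item in 8.8 |
|---|---|
| Arm fatigue | none |
| Soft-tissue discomfort | yes |
| Dizziness | yes |
| Headache | yes |
| Breach of confidentiality | yes |

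Four of five are covered (time inconvenience is left out of the count). The catch-all for complaints does not clearly close the gap: it is worded for complaints outside the anticipated risks, and fatigue is an anticipated risk. The soft-tissue item does not clearly close it either, since 2.4.1 names fatigue and soft-tissue discomfort as separate risks.

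**3. By what route would fatigue reach the review?**

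A symptom that appears or worsens during the study is an AE (8.1.1). It must be asked about (8.4.1), graded mild, moderate or severe (8.2.1), recorded with onset and resolution times (8.3) and entered in the database (14.1). Section 8.8 includes AE assessment in safety monitoring. So there is a route, but it is the general one.

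**4. Does the visit schedule put that route into practice?**

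The tables in 7.1 and section 20 each have seven rows: consent, eligibility, demographics, handedness, Fugl-Meyer, the VR task and neuroimaging. Neither has a row for symptoms or AEs. The narrative in 7.2 names only the open prompt at the end. Section 10.4.4 promises AE coding, but the table it gives lists the fields of a narrative report, not symptoms or grades.

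**5. What does a percentage need?**

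It needs the same question put to everyone in the denominator. With 12 participants planned per cohort, one participant is 1/12 = 8.3 percentage points. One person not asked, or one mild symptom not classed as an AE, therefore shifts a cohort percentage visibly.

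**The case against.** The strongest defence is that the AE system is complete. A reader might infer from 8.1 and the 8.8 list that the review would have no data on arm fatigue, would see only spontaneous complaints, or would have no measure of magnitude. The documents do not support any of these. The route in step 3 provides active questioning, a three-level grade and times of onset and resolution. Section 8.3 also treats conditions present at screening as baseline and counts deterioration as an AE, so pre-existing complaints are not ignored. This part of the defence stands.

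The 8.1 sentence can also be read narrowly, as meaning no safety endpoints, which 10.4.4 says as well. That may be what was intended. But the preceding sentence of 8.1 already says it, so the next one reads as a separate rule on recording. Rewording settles the matter either way.

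Two further inferences should be set aside. First, the earlier data cited in 8.1 are small. Treating them as zero events gives a one-sided 95% upper bound of 1 − 0.05^(1/14) = 19.3% for the 14 stroke participants, and 1 − 0.05^(1/26) = 10.9% if the 12 healthy controls are pooled with them. The arithmetic is right, but it would count against a plan to record nothing, and taken as a whole this is not such a plan. Second, skin abrasion has no line of its own in 8.8, but 2.4.1 gives skin as an example of soft-tissue discomfort, so it plausibly falls under the existing item.

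Finally, a study datasheet is listed in section 19 but is not in the reviewed text. It may have symptom fields. Section 19 says that attachments are not part of the protocol, so such fields would not remove the conflict with 8.1.

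**Conclusion.** The point holds as an internal contradiction and an omission. Section 8.1, as worded, conflicts with 8.3, 8.4.1, 8.8 and 14.1. Arm fatigue, the first-named device risk, is the one of five participant-level risks without an item in the list to be quantified. Its capture depends on general AE recording, which no row in either task table schedules.

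The size is modest. No endpoint, test or sample-size figure changes, and fatigue data would exist if 8.3 and 8.4.1 are followed. What is at risk is a safety review whose percentages do not rest on the same questions put to every participant. The conclusion assumes that 8.1 is read as written and that the unseen datasheet does not override the protocol.

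**What to change.** 1. Replace the 8.1 sentence with, for example: *The study has no safety endpoints. Adverse events and the symptoms listed in 8.8 are recorded for every participant.*
2. Add arm fatigue to the 8.8 list.
3. Add one symptom-check row to the tables in 7.1 and section 20. Each participant is asked about the listed symptoms before block 1 and after each of the three blocks, separately for each arm where the symptom concerns the arm, and answers are graded with the mild/moderate/severe scale of 8.2.1.

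This concerns measurement only and alters no device setting or rule on ending participation.

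**Cost.** Headache, dizziness, and fatigue and soft-tissue discomfort in each arm make 2 + 2 × 2 = 6 short answers at 4 time points, or 24 per participant. That is about a minute per break, and 2.4.1 already plans breaks every 5 minutes. The edits touch four sections and need IRB approval under 13.2. No staff or equipment is added. Direct questioning will probably raise the count of mild symptoms.

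**Limit.** Block order is fixed, so the loaded block always follows the baseline block. Differences between blocks will show when symptoms arose; they will not separate the effect of loading from accumulated fatigue or time in the headset, and the report should say so.
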